6.2. Detecting and recording serious adverse events

6.2.1. Time period for detecting and recording serious adverse events

In order to fulfill international reporting obligations, SAEs that are related to study participation (i.e. protocol-mandated procedures, invasive tests, a change from existing therapy) will be collected and recorded from the time the subject consents to participate in the study until she is discharged.

6.2.2. Evaluation of serious adverse events

6.2.2.1. Active questioning to detect serious adverse events

Each subject/subject's parent(s)/LAR(s) will be instructed to contact the investigator immediately should the subject manifest any signs and symptoms she perceives/they perceive as serious.

All SAEs either observed by the investigator or his/her staff or reported by the subject/subject's parent(s)/LAR(s) spontaneously or in response to a direct question will be evaluated by the investigator. The nature of each event, data and time (where appropriate) of onset, outcome, and relationship to the study procedures should be established.

When an SAE occurs, it is the responsibility of the investigator to review all documentation (e.g. hospital progress notes, laboratory, and diagnostics reports) relative to the event. The investigator will then record all relevant information regarding an SAE on the eCRF or SAE Report screens, as applicable. It is not acceptable for the investigator to send photocopies of the subject's medical records to GSK Biologicals instead of the appropriate completed SAE pages on the SAE screens in the eCRF. However, there may be instances when copies of medical records for certain cases are requested by GSK Biologicals. In this instance, all subject identifiers will be blinded on the copies of the medical records prior to submission to GSK Biologicals.

The investigator will attempt to establish a diagnosis pertaining to the event based on signs, symptoms, and/or other clinical information. In such cases, the diagnosis should be documented as the SAE and not the individual signs/symptoms.

6.2.2.2. Assessment of intensity

The investigator will assess the maximum intensity that occurred over the duration of the event for all SAEs reported during the study. The assessment will be based on the investigator's clinical judgement.

The intensity of each SAE recorded in the eCRF or SAE Report screens, as applicable, should be assigned to one of the following categories:

1 (mild) = An SAE which is easily tolerated by the subject, causing minimal discomfort and not interfering with everyday activities.

2 (moderate) = An SAE which is sufficiently discomforting to interfere with normal everyday activities.

3 (severe) = An SAE which prevents normal, everyday activities

In adults/adolescents, such an SAE would, for example, prevent attendance at work/school and would necessitate the administration of corrective therapy.

6.2.2.3. Assessment of causality

The investigator should assess the causality of each SAE. The investigator will use clinical judgment to determine the relationship of SAEs to study procedures. Alternative causes, such as natural history of the underlying diseases, concomitant therapy and other risk factors will be considered and investigated.

There may be situations when a SAE has occurred and the investigator has minimal information to include in the initial report to GSK Biologicals. However it is very important that the investigator always makes an assessment of causality for every event prior to submission of the SAE to GSK Biologicals. The investigator may change his/her opinion of causality in light of follow-up information, amending the SAE information accordingly.

If an event meets the criteria to be determined 'serious' (refer to Section 6.1.2), it will be examined by the investigator to the extent to enable determination of all contributing factors applicable to each SAE.

Possible contributing factors include:

- Medical history.
- Concomitant medication.
- Protocol required procedure.
- Other procedure not required by the protocol.
- Other cause (specify).

6.2.2.4. Assessment of outcomes

Outcome of any SAE reported during the entire study will be assessed as:

- Recovered/resolved.
- Recovering/resolving.
- Not recovered/not resolved.
- Recovered with sequelae/resolved with sequelae.
- Fatal.

6.3. Reporting of serious adverse events**6.3.1. Prompt reporting of serious adverse events related to a study procedure to GSK Biologicals**

SAEs that occur in the time period defined in Section 6.2.1 will be reported promptly to GSK within the timeframes described in Table 9 once the investigator determines that the event meets the protocol definition of a SAE.

Table 9 Timeframes for submitting SAEs

Type of Event	Initial Reports		Follow-up of Relevant Information on a Previous Report	
	Timeframe	Documents	Timeframe	Documents
SAEs related to a study procedure	24 hours ⁽¹⁾	SAE screen	24 hours ⁽¹⁾	SAE screen

⁽¹⁾ Timeframe allowed after receipt or awareness of the information.

6.3.2. Contact information for reporting serious adverse events and other events to GSK Biologicals

Please see the [Sponsor Information](#) Sheet for contact details.

Back-up Study Contact for Reporting SAEs
GSK Biologicals Clinical Safety & Pharmacovigilance
Fax: PPD or PPD
24/24 hour and 7/7 day availability

6.3.3. Completion and transmission of SAE reports related to a study procedure to GSK Biologicals

Once an investigator becomes aware that a SAE has occurred in a study subject, the investigator (or designate) must complete the information in the SAE screens of the eCRF **WITHIN 24 HOURS**. The SAE screens will always be completed as thoroughly as possible with all available details of the event. Even if the investigator does not have all information regarding a SAE, the SAE screens should still be completed within 24 hours. Once additional information is received, the SAE screens in the eCRF should be updated **WITHIN 24 HOURS**.

The investigator will always provide an assessment of causality at the time of the initial report.

6.3.3.1. Back-up system in case the electronic SAE reporting system does not work

If the electronic SAE reporting system does not work, the investigator (or designate) must complete, then date and sign a SAE Report Form and fax it to the GSK Biologicals Clinical Safety and Pharmacovigilance department within 24 hours.

This back-up system should only be used if the electronic SAE reporting system is not working and NOT if the system is slow. As soon as the electronic SAE reporting system is working again, the investigator (or designate) must complete the SAE screens in the eCRF within 24 hours. The final valid information for regulatory reporting will be the information reported through the electronic SAE reporting system.

6.3.3.2. Updating of SAE information after freezing of the subject's eCRF

When additional information is received on a SAE after freezing of the subject's eCRF, new or updated information is to be recorded on a SAE Report Form, with all changes signed and dated by the investigator. The updated form should be faxed to the GSK Biologicals Clinical Safety and Pharmacovigilance department or to the Study Contact for Reporting SAEs (refer to the [Sponsor Information Sheet](#)) WITHIN 24 HOURS of receipt of the follow-up information.

6.4. Follow-up of serious adverse events

After the initial SAE report, the investigator is required to proactively follow each subject and provide further information on the subject's condition to GSK Biologicals.

All SAEs documented at a previous visit/contact and designated as not recovered/not resolved or recovering/resolving will be reviewed at subsequent visits/contacts until the end of the study.

Investigators will follow-up subjects with SAEs until the event has resolved, subsided, stabilized, disappeared, or until the event is otherwise explained, or the subject is lost to follow-up.

Clinically significant laboratory abnormalities will be followed up until they have returned to normal, or a satisfactory explanation has been provided. Additional information (including but not limited to laboratory results) relative to the subsequent course of such abnormalities noted for any subject must be made available to the Site Monitor.

GSK Biologicals may request that the investigator performs or arranges for the conduct of additional clinical examinations/tests and/or evaluations to elucidate as fully as possible the nature and/or causality of the SAE. The investigator is obliged to assist. If a subject dies during participation in the study or during a recognized follow-up period,

GSK Biologicals will be provided with a copy of any available post-mortem findings, including histopathology.

7. SUBJECT COMPLETION AND WITHDRAWAL

7.1. Subject completion

A subject who returns for the concluding visit foreseen in the protocol is considered to have completed the study.

7.2. Subject withdrawal

Subjects who are withdrawn because of SAE must be clearly distinguished from subjects who are withdrawn for other reasons. Investigators will follow subjects who are withdrawn as result of a SAE until resolution of the event (see Section [6.3](#)).

From an analysis perspective, a ‘withdrawal’ from the study refers to any subject who did not come back for the concluding visit foreseen in the protocol.

All data collected until the date of withdrawal/last contact of the subject will be used for the analysis.

A subject is considered a ‘withdrawal’ from the study when no study procedure has occurred, no follow-up has been performed and no further information has been collected for this subject from the date of withdrawal/last contact.

Investigators will make an attempt to contact those subjects who do not return for scheduled visits or follow-up.

Information relative to the withdrawal will be documented in the eCRF. The investigator will document whether the decision to withdraw a subject from the study was made by the subject herself, by the subject’s parent(s) or LAR(s), or by the investigator, as well as which of the following possible reasons was responsible for withdrawal:

- SAE.
- Protocol violation (specify).
- Consent withdrawal, not due to an adverse event.
- Moved from the study area.
- Lost to follow-up.
- Death.
- Other (specify).

8. DATA EVALUATION: CRITERIA FOR EVALUATION OF OBJECTIVES

8.1. Endpoints

8.1.1. Primary endpoints

- Occurrence of CMV secondary infections determined in all seropositive subjects on samples collected during the 4-month Site Visits until study conclusion:
 - *Anti-CMV tegument protein IgG antibody concentration in serum (ELISA).*
 - *Number of CMV DNA copies (pp65 or other genes) in urine (qPCR).*

8.1.2. Secondary endpoints

- Occurrence of CMV primary infection determined in all seronegative subjects on samples collected during the 4-month Site Visits until study conclusion:
 - *Anti-CMV tegument protein IgG antibody concentration in serum (ELISA).*

8.1.3. Tertiary endpoints (amended 19 February 2015)

- Further characterization of primary infection in initially seronegative subjects during the 4-month Site Visits until study conclusion (testing done upon seroconversion) **might be done**:
 - *Number of CMV DNA copies (pp65 or other genes) in urine (qPCR).*
- Further characterization of primary and /or secondary CMV infections in a subset of subjects on selected samples of the Sample Collection Visits* **might be done**.
 - *Number of CMV DNA copies (pp65 or other genes) in urine (qPCR).*
 - *Number of CMV DNA copies (pp65 or other genes) in saliva (qPCR).*

* *In case of a positive sample at a 4-month Site Visit time point, testing-might be done on selected samples collected during the Sample Collection Visit.* The selection of samples to be tested will be based on the qPCR results obtained following the Site visits.

- Further characterization of primary and /or secondary CMV infections in a subset of subjects on all available samples of the 4-month Site Visits **might be done**:
 - *Anti-CMV tegument protein IgG antibody avidity index in serum (ELISA).*
 - *Anti-gB IgG antibody concentration in serum (ELISA).*
 - *Anti-gB IgG antibody avidity index in serum (ELISA).*
 - *Anti-CMV IgM antibody concentration in serum (ELISA).*
 - *Number of CMV DNA copies (pp65 or other genes) in saliva and blood (qPCR).*
 - *Assessment of anti-CMV neutralizing antibodies on different target cells and/or other virus strains.*

- Development of assays that will allow differentiating re-infection from re-activation from primary infection in a subset of subjects **might be done**.
 - *Characterization of CMV strains by genotyping/sequencing.*
 - *Exploring the CMV strain specific antibody profile using peptide microarrays.*
- Assessment of the expression of host genes* using techniques such as qPCR or mRNA microarray in a subset of subjects **might be performed**.
 - * excluding genes related to hereditary characteristics of the subject.
- Evaluation of the impact of demographic, social or behavioral factors upon CMV infection **might be performed**.
- Occurrence of congenital CMV infection in newborns of subjects who become pregnant during the study **might be evaluated**:
 - *Evidence of CMV DNA in urine and/or saliva of newborns within 10 days of delivery by using qPCR (pp65 or other genes) might be tested.*

8.2. Sample size consideration

The sample size for this study is not based on formal statistical considerations. The target is to recruit approximately 200 evaluable seropositive adolescent females. Considering a conservative incidence rate of CMV infection of 2% per year, it is expected that approximately 12 seropositive subjects will be re-infected during the study period.

A target number of approximately 200 evaluable seropositive adolescent females will be analyzed. Considering a 15-20% drop out rate during the 3-year study period, approximately 240 seropositive subjects will be enrolled.

Some laboratory assays will be performed on a subset. The subset will be defined based on the outcome of the primary/secondary endpoints or the development of the assay. The subset is the minimum number of subjects that will be tested. If applicable, all subjects could be tested.

8.3. Classification of cases (amended 19 February 2015)

- A **primary infection** is defined as the first infection with CMV in subjects who were seronegative at enrolment and will be evaluated by:
 - Appearance of anti-CMV tegument protein IgG antibodies in serum
AND/OR
 - Appearance of anti-gB IgG antibodies in serum
WITH or WITHOUT
 - Presence of CMV DNA in urine.

- CMV **re-infection*** with a different CMV strain in subjects who were seropositive at the time of enrolment will be evaluated by:
 - Appearance or increase of anti-CMV tegument protein IgG antibodies in serum
AND/OR
 - Appearance or increase of anti-gB IgG antibodies in serum
AND/OR
 - Appearance or increase of CMV DNA in urine
AND (*depending on assay availability*) in the presence of
 - Change in polymorphism in the antibody recognition profile in follow-up serum samples
AND/OR
 - Genotyping data characteristic of a re-infection
- CMV **re-activation*** of latent CMV in subjects who were seropositive at the time of enrolment will be evaluated by:
 - Appearance or increase of anti-CMV tegument protein IgG antibodies in serum
AND/OR
 - Appearance or increase of anti-gB IgG antibodies in serum
AND/OR
 - Appearance or increase of CMV DNA in urine
AND (*depending on assay availability*) in absence of
 - Change in polymorphism in the antibody recognition profile in follow-up serum samples
AND/OR
 - Genotyping data characteristic of a re-infection

* Depending on the future scientific knowledge and the data generated in this study multiple case definition might be explored.

8.4. Study cohorts to be evaluated

8.4.1. Total cohort

The **Total cohort** will include all subjects enrolled in the study.

8.4.2. According-to-protocol cohort (amended 19 February 2015)

The **according-to-protocol (ATP) cohort** will include all subjects who meet all inclusion criteria and no exclusion criteria for the study, who do not have any elimination criteria during the study (Section 5.5.2.9) and who comply with the study procedures.

A detailed, comprehensive list of reasons for elimination from ATP analyses will be established at the time of data cleaning.

8.5. Derived and transformed data

Immunogenicity

The cut-off value is defined by the laboratory before the analysis and is described in [Table 6](#).

- A seronegative subject is a subject whose titer is below the cut-off value.
- A seropositive subject is a subject whose titer is greater than or equal to the cut-off value.

For seronegative subjects, seroconversion is defined as the appearance of antibodies (i.e. titer greater than or equal to the cut-off value).

The geometric mean titers (GMTs) calculations will be performed by taking the anti-log of the mean of log titer transformations. Antibody titers below the cut-off of the assay will be given an arbitrary value of half the cut-off for the purpose of GMT calculation.

Virology

For seronegative subjects, CMV DNAemia is defined as the detection of CMV DNA (i.e. number of CMV DNA copies/mL is greater than or equal to the cut-off value).

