Upon primary infection of the mother during pregnancy (between 1.38% and 3.85% per year [Colugnati, 2007]), the transmission rate of the virus to the fetus is approximately 30% in contrast to seropositive women in whom vertical transmission has been estimated to be 1%. In countries or populations where high seropositivity rates are observed actually more cCMV infected babies will be born from secondary infections (re-infection/ re-activation) than from primary infections.

As pre-existing maternal immunity to CMV provide some protection against vertical transmission of the virus [Nyholm, 2010], primary maternal infection may place the child at higher risk of permanent and serious disabilities [Hyde, 2010]. It is generally believed that primary infections cause more severe disease than re-infections or re-activations [Fowler, 2003]. However, several investigators have also reported severe cCMV disease in babies born from seropositive mothers resulting in lifelong disabilities, mainly leading

to hearing loss [Boppana, 1999; Ross, 2006; Nyholm, 2010; Yamamoto, 2011; Mussi-Pinhata, 2009].

Some attempts have been made to evaluate the relative contribution of re-activation of latent virus or re-infection with a different CMV strain to intrauterine transmission of the virus to the infants born to women with pre-existing immunity. An enzyme-linked immunosorbant assay (ELISA) was developed to distinguish serological responses against infection with different CMV strains [Novak, 2008; Boppana, 2001]. The principle of this assay was based on the defined heterogeneity of antibody binding epitopes of glycoprotein H (gH) and/or glycoprotein B (gB) from two laboratory strains of CMV (AD169 and Towne). The detection of new antibody reactivity to either epitope on gH or gB in serum samples of seropositive women was considered as seroconversion and infection with a new virus strain (re-infection). One limitation of this assay is that not all CMV-specific IgG-positive individuals can be identified using these antigens. Specimens from more than a third of the seropositive individuals did not contain antibodies against any of the four antigenic determinants tested. This suggests the presence of additional polymorphic epitopes on gH and gB as well as on other envelope glycoproteins of CMV, such as glycoprotein N.

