3.1. Discussion of study design

The study sites will be selected in multiple countries, including countries where the CMV prevalence is assumed to be high in order to enroll primarily CMV seropositive adolescent females to allow the evaluation of CMV secondary infections. Since enrolment will proceed without previous CMV screening, some of the enrolled subjects will be seronegative. The enrolled seronegative subjects will allow the estimation of the incidence of CMV primary infections in the adolescent population.

To increase the probability to capture all CMV infections (primary and secondary infections), regular sample collection time-points have been arranged:

- **Site Visits:** Subjects will be asked to perform a Site Visit approximately every 4 months for 3 years (10 Site Visits in total). At Site Visits, blood, urine and saliva will be collected.
- **Sample Collection Visits:** Subjects will be contacted to perform urine and saliva sample collections at home either by self-collection or by a home visiting nurse. Alternatively subjects may be asked to come back to the study center where the investigator or designate will collect the samples. These Sample

Collection Visits will occur approximately every 4 months for 3 years between 2 Site Visits (9 Sample Collection Visits in total).

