2. STUDY DESIGN

This is a prospective, multi-center, multi-country study. In total, approximately 240 seropositive subjects whom anti-CMV IgG antibodies are detected in serum sample collected at Visit 1 and 160 seronegative subjects (10-17 years) whom anti-CMV immunoglobulin G (IgG) antibodies are not detected in serum sample collected at Visit 1. will be enrolled in this study.

Table 1 describes the difference between enrolment groups. Table 2 describes the time and events during the study.

Table 1 Study groups foreseen in the study

Study Groups	Number of subjects	Age (Min/Max)
S+	+/- 240 seropositive subjects	10 – 17 years
S-	Estimated approximate number of seronegative subjects ⁽¹⁾ : 160	10 – 17 years

⁽¹⁾ As subjects will be enrolled consecutively without previous CMV screening with a target number of 240 seropositive subjects, the number of seronegative subjects enrolled will depend on the seroprevalence of the participating countries.

Table 2 Time and Events Table – Follow-up Period (until 36 Month)

Time point							
	Year 1						
Month	M0	M2	M4	M6	M8	M10	M12
Site Visits	V1		V2		V3		V4
Sample Collection Visits		SCV1		SCV2		SCV3	
Year 2							
Month		M14	M16	M18	M20	M22	M24
Site Visits			V5		V6		V7
Sample Collection Visits		SCV4		SCV5		SCV6	
Year 3							
Month		M26	M28	M30	M32	M34	M36
Site Visits			V8		V9		V10
Sample Collection Visits		SCV7		SCV8		SCV9	
Samples:							
Blood	✓		✓		✓		✓
Saliva	✓	✓	✓	✓	✓	✓	✓
Urine	✓	✓	✓	✓	✓	✓	✓

In case of pregnancy resulting in live birth: Urine and or saliva from the newborn will be collected (if possible) as per standard of care in the center where the subject has delivered or through a home visiting nurse or alternatively, the subject may be asked to come back to the study center within 10 days of delivery.

Outline of study procedures

Table3 List of study procedures

Age	10-17 years						
Epoch	001						
	Year 1						
Time-point (Months)	M0	M2	M4	M6	M8	M10	M12
Visit/Sample Collection Visit	V1	SCV1	V2	SCV2	V3	SCV3	V4
	Year 2						
Time-point (Months)		M14	M16	M18	M20	M22	M24
Visit/Sample Collection Visit		SCV4	V5	SCV5	V6	SCV6	V7
	Year 3						
Time-point (Months)		M26	M28	M30	M32	M34	M36
Visit/Sample Collection Visit		SCV7	V8	SCV8	V9	SCV9	V10
Informed consent	●						
Check inclusion/exclusion criteria	●						
Record demographic data	●						
Record social and behavioral data ⁽¹⁾	●					●	●
Medical history	●						
CMV serostatus ⁽²⁾ (~3.5 to 5 mL)	●						
Blood sample ⁽³⁾							

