6.2.2. Analysis of secondary objective

Descriptive statistics will be provided for each secondary endpoint at each time point for which a sample is available and will include (not exhaustive) the following tabulations (with 95% CI):

- The percentage of CMV seronegative subjects with appearance of anti-CMV tegument protein IgG antibodies in serum.

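### One unconfirmed tegument IgG value at or above the cut-off can count as a primary infection, which can bias the secondary incidence upward by an amount set by an unstated assay specificity

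*Protocol*

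**What the plan says.** - **Seroconversion rule.** Protocol 8.5: "For seronegative subjects, seroconversion is defined as the appearance of antibodies (i.e. titer greater than or equal to the cut-off value"). No repeat sample, retest or second assay is mentioned.
- **Endpoint.** Protocol 8.1.2: "Occurrence of CMV primary infection determined in all seronegative subjects on samples collected during the 4-month Site Visits until study conclusion", judged on anti-CMV tegument IgG only. SAP 4.2 is the same.
- **Case definition.** Protocol 8.3 joins tegument IgG and gB IgG by AND/OR, and adds urine DNA as "WITH or WITHOUT". One tegument result is therefore sufficient.
- **Analysis.** SAP 6.2.2 tabulates, with 95% CI, "The percentage of CMV seronegative subjects with appearance of anti-CMV tegument protein IgG antibodies in serum". It has no rule for reversion to negative.
- **Schedule.** Protocol 3.1: "Subjects will be asked to perform a Site Visit approximately every 4 months for 3 years (10 Site Visits in total"). Protocol Table 8 has tegument IgG measured in all subjects at all of these visits.
- **Optional tests.** Protocol 8.1.3 lists gB IgG, avidity, IgM and urine PCR after seroconversion as tertiary work that may or may not be done. The amendment 1 rationale mentions gB in a subset as a way to confirm tegument results.
- **Assay performance.** Table 6 leaves the tegument cut-off to be determined. No specificity is given.

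**The concern.** The secondary objective is the incidence of primary infection, and the case rule feeds its numerator directly. A subject who is never infected has nine opportunities to cross the cut-off by chance. If any one crossing makes a case, errors accumulate over visits and can only add cases. The effect is proportionally largest where true incidence is low. The Clopper-Pearson interval in SAP Annex 1 covers sampling error and would not show this bias.

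The plan is more careful elsewhere. Grey-zone IgM samples are retested (Protocol Appendix A), and seropositive subjects need at least a 2-fold or 4-fold IgG rise (SAP 6.2.1). A seronegative subject needs no minimum rise, so moving from just below to just above the cut-off is enough. The next visit's serum would usually settle the matter and is already scheduled for testing, yet no rule uses it.

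**Working it through.** **The plan's own figure.** Protocol 8.2: "Considering a conservative incidence rate of CMV infection of 2% per year, it is expected that approximately 12 seropositive subjects will be re-infected". Check: 200 × 0.02 × 3 = 12.0, or 200 × (1 − 0.98³) = 11.8 as cumulative risk. It reproduces. The documents give no corresponding figure for seronegative subjects.

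**Inputs from the documents.**
- N = 160 (SAP 2: "160 seronegative subjects (10-17 years").
- Tests per subject: 10 Site Visits − 1 baseline = 9.
- Annual rate r: "between 1.38% and 3.85% per year" (Protocol 1.1, given for mothers in pregnancy). The 2% planning rate, stated for seropositive subjects, serves as a middle value.

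**Assumptions.** Per-test specificity of 99.9%, 99.5% or 99%; sensitivity 100%; no dropout.

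**True cases over 3 years**, 160 × (1 − (1 − r)³):
- r = 1.38%: 6.5
- r = 2%: 9.4
- r = 3.85%: 17.8

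**False cases, one-hit rule, independent errors**, 160 × (1 − spec⁹):
- 99.9%: 160 × 0.00896 = 1.4
- 99.5%: 160 × 0.0441 = 7.1
- 99%: 160 × 0.0865 = 13.8

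Removing subjects from risk once truly infected changes these little: about 1.4, 6.6 to 6.9, and 13.0 to 13.5 across the range of r.

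**False cases, correlated errors.** Let each subject's false-positive probability p follow a beta distribution with mean f = 1 − spec and within-subject correlation ρ (also an assumption). Condition on a negative Visit 1, because analysis serostatus is set there. Then the false cases are 160 × (1 − E[(1−p)¹⁰] / E[1−p]).

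| Specificity | Independent | ρ = 0.1 | ρ = 0.3 | ρ = 0.5 |
|---|---|---|---|---|
| 99.9% | 1.4 | 1.0 | 0.5 | 0.3 |
| 99.5% | 7.1 | 4.7 | 2.6 | 1.5 |
| 99% | 13.8 | 9.3 | 5.2 | 3.1 |

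**Where false equals true (independent errors).** With per-interval risk h = 1 − (1 − r)^(1/3), the counts match when f = h/(1 − h):
- r = 1.38%: h = 0.00462, specificity 99.5%
- r = 2%: h = 0.00671, specificity 99.3%
- r = 3.85%: h = 0.0130, specificity 98.7%

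**Two consecutive positives required, 99% specificity.** False cases fall to 0.13 with independent errors, and to 0.9, 1.2 and 1.0 at ρ = 0.1, 0.3 and 0.5. They are lower at higher specificity.

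**True cases lost if only a later serum can confirm.** Infections first seen at Visit 10 have no later serum. At 2% per year the count falls from 9.4 to 160 × (1 − 0.98^(8/3)) = 8.4, a loss of about one.

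**Dropout.** With 20% linear dropout, true and false counts both fall by about 11% and their ratio is unchanged.

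**The case against.** The strongest counter-argument is that the size is unknown. With specificity unstated and the cut-off still to be set by the laboratory, the problem could be small: at 99.9%, 1.4 or fewer false cases stand against 6.5 to 17.8 true ones. That stands.

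Independent errors are also the unfavourable case. Persistent cross-reactors would mostly be positive at Visit 1 and be classed as seropositive. This stands too. It lowers the one-hit count, and it weakens the benefit of confirmation, since a correlated error tends to repeat. A low-titre true seropositive misread as negative at Visit 1 would pass any confirmation rule.

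The rate range is borrowed from pregnancy, while this study enrols girls aged 10 to 17 in high-prevalence countries. A higher true rate would shrink the false share.

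SAP 6.2.2 tabulates by time point and defines no ever-positive algorithm. On a purely per-visit table, false positives at 99% would be about 160 × 0.01 = 1.6 per visit. However, the endpoint runs to study conclusion and the objective is incidence, so a cumulative count is the natural reading. The text is unclear rather than protective.

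The plan is not without means of confirmation. Viral load testing in seronegative subjects is tied to seroconversion (Protocol 5.6.3), SAP 6.2.3 tabulates urine DNA in them, and gB may be used. All of this is optional, and none of it changes who counts as a case. That the analyses are descriptive (SAP 7) does not remove bias from an estimate that is itself an objective.

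**Conclusion.** The rule as written allows a primary infection to be counted on one tegument IgG value with no required confirmation, and this can bias the secondary incidence upward. Under the assumptions above the excess runs from about 0.3 cases (99.9%, ρ = 0.5) to about 14 (99%, independent errors), against roughly 6.5 to 17.8 true cases if the pregnancy rates carry over to these adolescents.

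A reader might infer that false seroconversions will match or outnumber true ones. The documents do not support that. It needs a specificity of roughly 99.5% to 98.7% or lower, depending on incidence, together with near-independent errors. At 99% and ρ = 0.1, for example, 9.3 false cases exceed 6.5 true ones, but at ρ = 0.3 the 5.2 do not. A reader might also infer that confirmation almost abolishes false cases. The 0.13 holds only for independent errors; about 1 remains with correlation.

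This is a correction that should be made, with medium confidence about its size. The gap in the rule is plain in the text, the magnitude is conditional, and the remedy is cheap.

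**What to change.** In Protocol 8.3 and 8.5 and SAP 6.2.2, use confirmed seroconversion as the incidence numerator. Section 8.3 must be included, or the protocol would hold two definitions. Confirmed means a tegument IgG value at or above the cut-off plus:
- the next available Site Visit serum at or above the cut-off; or
- when the first positive is the subject's last available sample (Visit 10, or earlier after dropout), gB IgG at or above its cut-off or CMV DNA in urine.

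Report unconfirmed and reverting single positives as a separate row, and keep the any-positive percentage beside the confirmed one as a sensitivity analysis. State the tegument cut-off and its specificity once known, since these decide how much the rule matters.

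The cost is wording plus gB ELISA, and urine PCR where not already done, on a few last-sample converters. No new visits are needed. The downside is that a few true cases first seen at the last sample may stay unconfirmed: about 1 of 9.4 at 2% per year if only a later serum were accepted, and fewer with the gB and urine routes. Those routes bring false positives of their own. They are not quantified here because the documents give no specificity for them, and the two-consecutive figures above do not cover them.
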